### 7.1.2.2. Laboratory Tests

Values for out of pre-defined clinically relevant will have clinically relevant values flagged set (L=Lower than normal range, H=Higher than normal range or A=Abnormal).

### 7.1.2.3. 12-Lead ECG

(1) Criteria for pre-defined limit

12-lead ECG:

- QTcF > 500msec
- 500 >= QTcF > 480msec
- 480 >= QTcF > 450msec
- QTcF <= 450 msec
- Change from baseline in QTcF > 30 msec
- Change from baseline in QTcF > 60 msec

### 7.1.3. Pharmacokinetics Evaluation

#### 7.1.3.1. Plasma Concentration

For the calculation of the summary statistics, concentration values reported as below the limit of quantification (BLQ) will be set to 0.

#### 7.1.3.2. Pharmacokinetic Parameters

(1) Below the limit of quantification

For the calculation of PK parameters, actual sampling time (in hours rounded to 3 DPs) relative to dosing should be used. Concentration below the limit of quantification (BLQ) will be imputed with a value of 0. For calculation of AUCs, missing data will be treated as if the respective sample never had been scheduled for the calculation by the linear-linear trapezoidal

rule. For Ae, Ae% and CLR, geometric mean and geometric CV% will be calculated only when all the individual Ae, Ae% and CLR is greater than 0 in each sampling time point.

## 7.2. Analysis Visit Definitions

### (1) Non-PK related

The date of the first dose of study drug is defined as Day 1.

Except for laboratory, baseline will be the last observed value of the parameter of interest prior to the first intake of study drug by each treatment period (this includes unscheduled visits).

For laboratory, baseline will be the last observed value of the parameter of interest prior to the first intake of study drug (this includes unscheduled visits).

No analysis visit window will not be performed for safety evaluation.

### (2) PK related

The allowable time window will be the following.

After administration of Edaravone oral suspension

Nominal Time Point	Window
Predose	Within 60 min before dosing
0.083 h after dosing	Nominal time point ± 1 min
0.25, 0.5, 0.75, 1, 1.5, 2, 4, 6, 8, 10, 12 h after dosing	Nominal time point ± 5 min
24, 36, 48 h after dosing	Nominal time point ± 15 min

After administration of Edaravone intravenous formulation

Nominal Time Point	Window
Predose	Within 60 min before dosing
0.25, 0.5 h after dosing	Nominal time point ± 5 min
1 h after dosing	End time of dosing + 0-1 min
1.083 h after dosing	End time of dosing + 4-6 min
1.25 h after dosing	End time of dosing + 10-20 min
1.5, 1.75, 2, 3, 4, 6, 8, 10, 12 h after dosing	Nominal time point ± 5 min
24, 36, 48 h after dosing	Nominal time point ± 15 min

## 7.3. Data Handling Convention for Missing Data

### (1) Non-PK related

Adverse events:

If severity or relationship is found to be missing the most severe occurrence will be imputed for the summary of interest.

Other safety:

For safety summaries, only observed data will be used. Unless otherwise specified, missing safety data will not be imputed.

### (2) PK related

For PK summaries, only observed data will be used. Missing plasma concentration data will not be imputed. When calculating Ae and Ae%, missing urine concentration data will be imputed to 0.

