|--------|--------|-------------|--|
| Perio | d I | Day 1 | Before administration of edaravone intravenous |
| | | · | formulation |
| | | | 0.25, 0.5, 1, 1.083, 1.25, 1.5, 1.75, 2, 3, 4, 6, 8, and 12 |
| | | | hours after administration |
| | | Day 2 | 24 and 36 hours after administration of edaravone |
| | | · | intravenous formulation |
| | | Day 3 | 48 hours after administration of edaravone intravenous |
| | | | formulation |
| Perio | d II | Day 4 | Before administration of edaravone oral suspension, |
| | | • | 0.083, 0.25, 0.5, 0.75, 1, 1.5, 2, 4, 6, 8, 10, and 12 hours |
| | ļ | | after administration |
| | | Day 5 | 24 and 36 hours after administration of edaravone oral |
| | | - | suspension |
| | | Day 6 | 48 hours after administration of edaravone oral suspension |
| | | | |

- (b) Frequency of blood sampling: 33
- (c) Volume of blood sampling: 5.5 mL, Total: 181.5 mL (per subject)

9.2.4.2 Measurement of urine concentrations of unchanged edaravone, sulfate conjugate, and glucuronide conjugate

Urine volume will be measured at voiding and the urine specimen will be processed (see Section 9.2.4.3). Urine will be forced to void before administration, 24 hours after administration, and 48 hours after administration.

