10.1 Pharmacokinetics

Plasma concentrations of unchanged edaravone, sulfate conjugate and glucuronate conjugate will be measured to calculate confirmatory PK parameters and reference PK parameters, AUC_{0-t} , AUC_{0-24} , $AUC_{0-\infty}$, C_{max} , t_{max} , $t_{1/2}$, Kel, MRT,* CL* or CL/F,* V_z * or V_z/F ,* V_s * or V_s/F ,* and F* (*: calculate only for unchanged edaravone) by non-compartmental analysis. Urine concentration will be measured to calculate Ae, Ae%, and CLr* or CLr/F* (*: calculate only for unchanged edaravone). The detailed calculation method for each parameter will be described in the Statistical Analysis Plan.

The drug concentration measurement site will separately create a protocol for plasma concentration measurement by the start of measurement and perform measurement according to it. The site will create a measurement result report.

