13.3 Data Handling

The data will be handled as described below, except for cases determined in the sponsor's data review meeting or at the meeting for the handling of drug concentration data. The handling of the safety and drug concentration data will be specified in the Statistical Analysis Plan or the Clinical Study Report.

(1) Handling of PK data

The acceptance time range for each blood sampling timepoint for determining the plasma drug concentrations will be specified in the Statistical Analysis Plan. The sponsor will judge the handling of the following data, as to whether or not to include them in the tabulation and analysis of the drug concentrations: (1) data that was collected from a blood specimen drawn outside of the acceptance time range; (2) data for which the plasma drug concentration was unmeasurable; and, (3) data for which a protocol deviation occurred, such as non-compliance with plasma collection procedures. The handling of data will be decided at the data review meeting or at the meeting for the handling of PK data.

(2) Handling of analysis visit

The acceptable time range for each measurement time point will be specified in the Statistical Analysis Plan, and the data collected within the time range will be used. Data will not be imputed by data collected outside the time range. If multiple data exist within the same time range for one assessment item, the data collected later will be used.

(3) Handling of unmeasurable data and reference data in laboratory tests

If unmeasurable or reference data are obtained due to specimen problems, etc., they will be handled as missing data.

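### SAP 7.3(2) sets every missing urine concentration to 0 for Ae and Ae%, which is right when nothing was voided but counts a voided sample with no result as zero excretion (reference parameters only)

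*SAP*

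**What the plan says.** - SAP 7.3(2), on urine: "When calculating Ae and Ae%, missing urine concentration data will be imputed to 0". No condition on the cause is attached, and no other section confines the rule to intervals without a void.
- SAP 7.3(2), the sentence just before: "Missing plasma concentration data will not be imputed".
- SAP 7.1.3.2, on values below the limit of quantification: "Concentration below the limit of quantification (BLQ) will be imputed with a value of 0". On gaps in the plasma profile when AUC is calculated: "missing data will be treated as if the respective sample never had been scheduled".
- Protocol 9.2.4.2: "Urine volume will be measured at voiding and the urine specimen will be processed", and "Urine will be forced to void before administration, 24 hours after administration, and 48 hours after administration". The schedule footnotes in Protocol 9.1 confirm that volume is taken at every void. Protocol 9.2.4.3 provides for backup urine specimens.
- Protocol 10.1: "Urine concentration will be measured to calculate Ae, Ae%, and CLr". Renal clearance is calculated for unchanged edaravone only.
- SAP Appendix 1 defines Ae as concentration times volume, Ae% as Ae over dose times 100, and CLr or CLr/F as Ae over AUC0-∞.
- SAP 2.1.2 lists Ae, Ae%, CLr and CLr/F as reference parameters.

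**The concern.** A urine concentration can be absent for two different reasons. If the subject passed no urine, nothing was excreted and zero is the true amount. If the subject passed urine, the volume was recorded and the sample then gave no result, the amount is unknown and will usually be positive. The SAP treats both alike.

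BLQ results already have their own zero rule, so the sentence in 7.3(2) is not needed for them. In the second case its effect is to replace an unknown amount with the lowest possible one. The error has a known sign: Ae, Ae% and CLr or CLr/F can only be too low. If the result is lost in one period only, the oral/IV ratio moves down for an oral loss and up for an IV loss.

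There is a side effect. Under SAP 7.1.3.2 the geometric mean and geometric CV% of Ae, Ae% and CLr are calculated only when all individual values at a time point exceed 0. If an imputed zero left one subject with Ae of 0 at a time point, those statistics would be dropped there for the whole group.

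**Working it through.** The plan states no figure for this rule, so there is none to reproduce.

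**Inputs from the documents.** Ae = sum over voids of concentration × volume (SAP Appendix 1); 42 subjects planned and 36 after the expected dropouts (Protocol 6.1); forced voids at 24 h and 48 h (Protocol 9.2.4.2).

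**Assumed inputs.** f, the share of a subject's Ae held in the lost void, and s, the within-subject SD on the log scale for a urinary parameter. The documents give neither.

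**Step 1: one void.** With the concentration set to 0, a void of any volume V contributes 0 × V = 0. With no void, V = 0 and the true contribution is also 0, so the rule does no harm there.

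**Step 2: one subject.** Reported Ae = (1 − f) × true Ae. Ae% and CLr or CLr/F are proportional to Ae, so they fall by the same fraction f.

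**Step 3: the oral/IV ratio.** In the balanced log-scale crossover analysis each of n subjects carries weight 1/n. One affected subject multiplies the geometric mean ratio by exp(ln(1 − f)/n) for an oral loss, and by the inverse for an IV loss.

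| n | f | Oral void lost | IV void lost |
|---|---|---|---|
| 42 | 1% | 0.99976 | 1.00024 |
| 42 | 5% | 0.99878 | 1.00122 |
| 42 | 10% | 0.99749 | 1.00251 |
| 42 | 25% | 0.99317 | 1.00687 |
| 42 | 50% | 0.98363 | 1.01664 |
| 36 | 10% | 0.99708 | 1.00293 |
| 36 | 50% | 0.98093 | 1.01944 |

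For f of 10% to 50% the shift is about 0.3% to 1.7% with 42 subjects and 0.3% to 1.9% with 36. For f of 1% to 5% it is 0.02% to 0.12% with 42.

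**Step 4: what leaving the subject out would cost.** The standard error rises by a factor √(42/41) = 1.012, or √(36/35) = 1.014. The variance of the log ratio is 2s²/n, so exclusion adds 2s²/(n(n − 1)). Zero imputation adds squared bias (ln(1 − f)/n)². The two are equal when |ln(1 − f)| = s√(2n/(n − 1)). With n = 42 the multiplier is √(84/41) = 1.431, which gives:

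- s = 0.10: f = 13.3%
- s = 0.20: f = 24.9%
- s = 0.30: f = 34.9%

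Below these shares, keeping the understated value gives the smaller mean squared error.

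**The case against.** **No case is shown.** SAP 6.3 reports that the data review meeting excluded no subject and judged all PK data valid except one out-of-window sampling. Backup urine specimens make a lost result less likely. This stands. SAP 6.3 does not say that every urine result was present, but a reader who infers that a missing result distorted this trial goes beyond the documents.

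**The rule may be meant for intervals without a void.** The documents do not say how such an interval is recorded. If volume and concentration are both blank, a zero rule is needed to compute the product, and it gives the right answer. That may well be the purpose. The sentence nevertheless also covers lost results.

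**The data meetings could handle it.** Protocol 13.3 allows exceptions decided in the sponsor's data review meeting or "at the meeting for the handling of drug concentration data". Its third item gives non-compliance with plasma collection as an example of a deviation, so reading the section as closed to urine would be too narrow. This stands in part: a meeting could have ruled on urine, but the written default still does not separate the two cases, and SAP section 1 gives the SAP precedence on analysis details.

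**The oral/IV comparison of urinary parameters is inferred.** SAP 8.4.1 promises only listing and summary by formulation for them, and SAP 8.4.2 names no urinary parameter among its examples. Protocol 13.4.2 does extend the same analysis in principle to the other reference parameters, so the comparison is the natural reading, but it is not spelled out.

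**The contrast with plasma proves nothing.** This is correct. A trapezoid spans a gap, whereas in a sum a dropped term and a zero give the same low total. A reader might infer that the plasma rule should be copied to urine; that would not correct Ae.

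**Excluding the affected subject may do more harm than good.** Step 4 supports this for small voids, so compulsory exclusion is not warranted.

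**Conclusion.** The rule as written is wrong for urine that was voided and measured but has no concentration result, and right for an interval with no void. In the first case the subject's Ae and Ae%, and for the parent drug CLr or CLr/F, are understated by f. For one affected subject of 42 and f between 10% and 50%, the oral/IV geometric mean ratio shifts by about 0.3% to 1.7%. This is conditional on a result being lost, on the assumed f, and on urinary parameters entering the oral/IV comparison.

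A reader might infer that the bioequivalence conclusion or absolute bioavailability is at risk. The documents do not support that: SAP 8.4.2 rests the decision on plasma AUC0-t, AUC0-∞ and Cmax, and SAP Appendix 1 computes F from AUC0-∞ and dose. This is a point to consider, confined to reference parameters.

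**What to change.** Replace the urine sentence in SAP 7.3(2) with:

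> The amount excreted is set to 0 only when no urine was voided or the concentration is BLQ. If a voided sample has no concentration result after any assay of the backup specimen, Ae for that interval is set to missing, and later cumulative Ae, Ae% and CLr or CLr/F are listed and flagged as incomplete (lower bounds). If any value is flagged, the summaries and the oral/IV comparison of these reference parameters are shown with and without the flagged values.

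Showing both versions avoids choosing in advance between a small downward bias and a lost subject. With forced voids at 24 h and 48 h, a loss after 24 h leaves the 0–24 h value intact, while a loss before 24 h flags both cumulative values.

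The cost is a short SAP text change, a small programming change and, only if a result is missing, one extra table. In the version without flagged values, one subject fewer of 42 raises the standard error by about 1.2%. The SAP is marked as its final version. If data lock has passed, which the documents do not show, Protocol 13.5 also requires a revised SAP, a stated reason, and separate presentation of results before and after the change. If no urine result was missing, no reported number changes.

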## 8. STATISTICAL METHODOLOGY

### 8.1. Study Subjects

#### 8.1.1. Subject Disposition

Subject disposition will be summarized on the SAF and listed on the enrolled subjects.

#### 8.1.2. Analysis Populations

Analysis populations will be summarized. Analysis populations including the inclusion and exclusion criteria deviation at screening listed on the all enrolled subjects.

#### 8.1.3. Study Drug Exposure

Exposure data will be summarized and listed on the SAF.

#### 8.1.4. Demographic and Other Baseline Characteristics

The following demographic and other baseline characteristics will be used.

	category	Descriptive
Sex	Male, Female	
Age(years)		Yes
Height(cm)		Yes
Weight(kg)		Yes
BMI(kg/m  )		Yes
Race	Japanese	
Medical History	No (if 'Never'), Yes (if otherwise)	
Complication	No (if 'Never'), Yes (if otherwise)	
Concomitant Medication	No (if 'Never'), Yes (if otherwise)	
Allergic History (including drug allergies)	No (if 'Never'), Yes (if otherwise)	
Drinking Status	No (if 'Never'), Yes (if otherwise)	
Smoking Status	No (if 'Never'), Yes (if otherwise)	

Demographic and other baseline characteristics will be summarized and listed on the SAF.

#### **8.1.5. Medical History and Allergic History**

Medical history and allergic history will be listed on the SAF.

#### **8.1.6. Prior or Concomitant Medications**

Prior and concomitant medication will be listed on the SAF.

### **8.2. Efficacy Assessments**

N/A

### **8.3. Safety Assessments**

All safety assessments will be consisted on the SAF.

#### **8.3.1. Adverse Events**

Overall summary for the following category will be conducted by treatment.

- Subjects with at least one AE
- Subjects with at least one adverse drug reaction
- Subjects with at least one SAE
- Subjects with at least one serious adverse drug reaction
- Subjects with at least one AE leading to discontinuation of study drug
- Subjects with AE leading to death

The following summaries also will be conducted by treatment. These tables will be ordered by International Agreed Order for SOC and then by alphabetical order for PT.

- AEs by SOC and PT
- Adverse drug reactions by SOC and PT
- AEs by SOC, PT and severity

Each of the summaries will be done at the subject level - multiple occurrences of the same event within a subject will be counted once in the summaries by SOC and PT; multiple occurrences of the same event within a subject will be counted once in the maximum severity category (severe > moderate > mild) and/or maximum drug relationship category (reasonable possibility/no reasonable possibility) and/or the earliest duration.

All AEs will be listed.

#### **8.3.2. Laboratory Tests**

Absolute values and changes from baseline, except for urinalysis will be summarized descriptively by group and scheduled visit.

For urinalysis, number and percentage will be presented. Shift tables will present the changes in clinically relevant categories from baseline to each scheduled post-baseline visit by group.

Below is a list of the laboratory test.

Laboratory Test	Parameters
Hematology	Hemoglobin, hematocrit, red blood cell count, white blood cell count, platelet count, MCH, MCHC, MCV, differential white blood count
Biochemistry	Na, K, Cl, Ca, inorganic phosphorus, urea nitrogen, creatinine, uric acid, total bilirubin, direct bilirubin, ALT, AST, $\gamma$ -GTP, ALP, LDH, CK, amylase, total cholesterol, triglycerides, LDL-C, HDL-C, total protein, albumin, glucose
Coagulation test	Prothrombin time, activated partial thromboplastin time
Urinalysis	Qualitative tests (pH, specific gravity, protein, glucose, occult blood, urobilinogen, bilirubin, ketones)

All data including clinically relevant flagged will be listed. Any BLQ data will be treated as 0 in summary statistics.

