13.4.1 Analysis of demographic characteristics and other baseline characteristics of the subjects

Regarding the following items about demographic characteristics and other baseline characteristics, frequency and percentage will be calculated for the discrete values, and descriptive statistics will be calculated for the numerical data. The calculation will be made for each group.

Assessment item: age, sex, height, body weight, BMI, race, medical history, complications, and concomitant medications

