13.4.3 Safety

(1) Adverse events and adverse drug reactions

Adverse events will be coded according to MedDRA (version 21.0 or higher). The number of subjects with and incidence rates of adverse events and adverse drug reactions will be calculated for each administration of edaravone oral suspension or edaravone intravenous formulation.

CONFIDENTIAL

(2) Vital signs and laboratory tests

For vital signs (systolic and diastolic blood pressure, pulse rate, and body temperature) and laboratory data (hematology, biochemistry, coagulation test, and urinalysis), descriptive statistics will be calculated for the values at each time point and the changes from baseline. The calculation will be done for administration of edaravone oral suspension and that of edaravone intravenous formulation each. Urinalysis data will be presented on shift tables for administration of edaravone oral suspension and that of edaravone intravenous formulation each.

(3) 12-lead ECG

For 12-lead ECG, descriptive statistics of the values at each time point and the changes from baseline will be calculated for administration of edaravone oral suspension and that of edaravone intravenous formulation each.

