#### 3.2. Study Design

##### 3.2.1. Type and Details of Cohorts

Single-dose, randomization, open-label, crossover study

Subjects	Period I	Period II
Advance administration of Edaravone oral suspension group (21 subjects)	Edaravone oral suspension 105 mg	Edaravone intravenous formulation 60 mg
Advance administration of Edaravone intravenous formulation group (21 subjects)	Edaravone intravenous formulation 60 mg	Edaravone oral suspension 105 mg

Forty-two subjects are randomly allocated to two groups of 21 subjects. It is carried out by the two-period, two-sequence crossover, randomization, open-label study. The duration of hospitalization will be 7 days and 6 nights.

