### 9.2. Treatments to Report

Treatment	For TFLs
Advance administration of Edaravone oral suspension group	PO – IV
Advance administration of Edaravone intravenous formulation group	IV – PO
Edaravone oral suspension	PO
Edaravone intravenous formulation	IV

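### Does planning the laboratory tables by group, where the protocol asks for each formulation, leave the safety reporting short?

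*SAP*

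**What the plan says.** Protocol 13.4.3(2) sets the content of the vital-sign and laboratory tables: "descriptive statistics will be calculated for the values at each time point and the changes from baseline". It then fixes the unit of summary: "The calculation will be done for administration of edaravone oral suspension and that of edaravone intravenous formulation each". Urinalysis has its own sentence: "Urinalysis data will be presented on shift tables for administration of edaravone oral suspension and that of edaravone intravenous formulation each".

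SAP 8.3.2 keeps the content but words the unit differently. For quantitative tests: "Absolute values and changes from baseline, except for urinalysis will be summarized descriptively by group and scheduled visit". For urinalysis: "Shift tables will present the changes in clinically relevant categories from baseline to each scheduled post-baseline visit by group". No section of the SAP defines *group* as a reporting unit. SAP 8.3.1, 8.3.3 and 8.3.4 plan adverse events, vital signs and ECG by treatment.

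Three other places govern how the two documents fit together. SAP 1 lets the SAP's analysis details override the protocol's. SAP 10 reports no departures from the protocol. Protocol 13.5 requires any change made before data lock to be stated with its reason in the SAP and the study report.

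**The concern.** Of the four listed safety assessments, only laboratory tests are not planned by treatment, and the different word appears in both sentences. Elsewhere *group* tends to mean sequence. SAP 3.2.1 has "Forty-two subjects are randomly allocated to two groups of 21 subjects", and those groups are the two orders of administration. In SAP 9.2 the word appears only in the sequence labels, for example "Advance administration of Edaravone oral suspension group". Protocol 13.4.1 says of the baseline tables "The calculation will be made for each group", whereas 13.4.3 speaks of each administration.

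On that reading the SAP drops the by-formulation laboratory tables that the protocol promises, overrides the protocol by its own rule in SAP 1, and does not declare the change. A reader looking for a laboratory signal after the oral suspension would not find one table that shows it.

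**Working it through.** No power, alpha or sample-size figure is involved. The check is what each reading of *group* would produce.

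**Step 1: how firm is the sequence reading?**

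- For sequence: SAP 3.2.1, the labels in SAP 9.2, Protocol 13.4.1, and SAP 7.2, which gives laboratory tests alone a single baseline before the first dose.
- For formulation: SAP 6.1 defines the percentage denominator by treatment group. SAP 9.2 lists PO-IV, IV-PO, PO and IV together in one column headed Treatment, so *treatment* and *group* are not cleanly separated terms in this SAP. SAP 10 says nothing has changed, and Protocol 13.1 describes the protocol as giving the minimum procedures, with the detail left to the SAP.

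Both readings are tenable. On the formulation reading there is no discrepancy beyond an undefined word.

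**Step 2: what would a by-sequence table contain?** SAP 9.3 schedules laboratory tests on Day 3 and Day 6, each 48 hours after a dose.

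| Sequence (at most 21 each) | Day 3 | Day 6 |
|---|---|---|
| PO-IV | after oral; change spans one dose | after intravenous; change spans two doses |
| IV-PO | after intravenous; change spans one dose | after oral; change spans two doses |

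Each of the 2 × 2 = 4 cells follows one known formulation. The oral data are PO-IV Day 3 plus IV-PO Day 6, 21 + 21 = at most 42. The intravenous data are IV-PO Day 3 plus PO-IV Day 6, again at most 42. The end-of-study sample follows both doses, so it belongs to no single formulation under either layout.

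**Step 3: is anything lost?** Counts and shift-table entries add. Minimum and maximum are read directly from the two cells. The mean is (n1·m1 + n2·m2)/(n1 + n2), which is (m1 + m2)/2 when both cells hold 21. With m the combined mean, the variance is [(n1−1)s1² + (n2−1)s2² + n1(m1−m)² + n2(m2−m)²]/(n1 + n2 − 1), exact up to reporting rounding. The median cannot be combined from two cells, but SAP 8.3.2 lists all laboratory data, so it can be computed from the listings.

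**Step 4: which layout suits the baseline?** SAP 7.2 gives vital signs and ECG a new baseline in each period, and laboratory tests one baseline before any dosing. With that baseline, a Day 3 change reflects one dose and a Day 6 change reflects two. A pooled by-formulation cell would mix up to 21 of each. The sequence-by-visit layout keeps them apart.

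**Step 5: would a clinically relevant abnormality go unseen by formulation?** Protocol 9.2.5.2 has the investigator treat clinically significant abnormal findings as adverse events, either in their own right or through the related sign or symptom. SAP 8.3.1 tabulates adverse events by treatment.

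**The case for a change.** The strongest case for a change is that some wording is owed on either reading. If *group* means sequence, Protocol 13.5 calls for the change and its reason to be written down, and SAP 10 has no such entry. If it means formulation, a programmer meets an undefined word that elsewhere labels sequences. The repair would cost a few words and one set of table shells, and the word occurs twice, so a single slip is less likely.

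The mismatch stands, and so does the possible missing line in SAP 10. Two things weaken the rest. First, the undeclared departure rests on adopting the sequence reading and then using it to make SAP 10 wrong, although the no-change statement is itself evidence that the protocol's unit was meant to carry over. One word carries limited weight in a text with other slips, such as the misspelt vital-signs heading and the double negative on visit windows in SAP 7.2. Second, a required by-formulation table would mix one-dose and two-dose changes, so it would need a caveat and would still need the sequence-by-visit tables beside it. It would be a rearrangement of data already reported.

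**Conclusion.** No change to the planned analysis is called for. On the formulation reading nothing differs from the protocol. On the sequence reading the effect is one of presentation: cells of at most 21 instead of 42, each in-period cell traceable to one formulation, and every statistic recoverable from the tables and listings. That layout is a fair choice given the single laboratory baseline. The tables are descriptive safety output, no test or decision rule uses them, and the bioequivalence result cannot move.

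This conclusion assumes that table headings identify sequence and visit, which the labels in SAP 9.2 and 9.3 provide for, and that the laboratory listings are produced as planned. What remains is a matter of record: an undefined term, or a layout choice to be named in the study report, which Protocol 13.5 would also expect to see in SAP 10 if sequence was intended.
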